8.4 Documentation and Reporting of Serious Adverse Events

SAEs will be reported to C5Research within 24 hours of learning of the event. The causality of the SAE (the relationship to the study treatment/procedures) will be assessed by the investigator. The SAE will also be documented on the appropriate eCRF.

Since the use of Ketamine in the ELEKT-D study is exempted from IND reporting, the Investigator does not have the responsibility to report any AEs/SAEs to the FDA.

8.5 Pregnancy

All pregnancies should be reported to C5Research within 24 hours of becoming aware of the pregnancy.

• Maternal exposure – If a patient becomes pregnant during the course of the study, study treatment will be continued or discontinued per investigator discretion. If any pregnancy occurs in the course of the study, the investigator

- must inform C5Research within 24 hours of awareness of the pregnancy.
- Paternal exposure There are no known risks regarding fathering a child while receiving either ECT or ketamine treatment. But, since there is limited data on ketamine in pregnancy it is advised that patients practice adequate birth control while in the study.

9. Statistical Plan

The key exposures of this study are alternate day ECT treatment and twice a week ketamine infusion. We will conduct an intention to treat (ITT) analysis. A sensitivity analysis will be performed on the modified intention-to-treat (mITT) population defined as a randomized patient having at least one treatment and one valid QIDS- SR16 measurement during the acute treatment phase. Percent of responders is the primary outcome in this study. A responder is defined as a subject with a ≥50% decrease from baseline in the primary endpoint (QIDS-SR-16).

Multiple imputations may be implemented to achieve completeness of the data. In an unlikely case that missing data are non-ignorable, pattern-mixture modeling will be applied.

As a general principle, the statistical analysis will follow the pre-specified statistical analysis plan (SAP). The SAP will be finalized prior to the end of the study. The SAP will address how missing data will be handled.

The primary outcome measure of response rate will be compared between ketamine and ECT using a chi-square test. A multivariable logistic regression model will be constructed, to account for potential heterogeneity of treatment effect caused by confounding variables. A similar analytic strategy will be applied to evaluate cognitive function and quality of life.

Sample size

The sample size justification will be for the primary outcome measure of response rate. Historical data reveal that the overall response rate as well as the respective response rate of ketamine and of ECT is around 50% - 60% on various scale measurements in patients with treatment-resistant depression. Assuming an observed difference of 10% and an acceptable difference margin of 5% with a 1-sided alpha=0.025, a sample of 400 patients (200 per group) provides 81.8% power to detect a treatment response, based on the Farrington-Manning score test of risk difference. The total sample also considers a 10% attrition rate.

10. Study Committees

The following committees will be responsible for the management of the study and the monitoring of the safety of the study patients.

Confidential Page **30** of **40** Protocol V7.0 16Feb2022

10.1 Executive Committee

The Executive Committee (EC) will have scientific responsibility for the study. They will review study conduct and progress, consider recommendations from the Data and Safety Monitoring Board (DSMB), and resolve any other study related issues. The EC will serve as the publishing committee for the study. The EC Charter document will guide the conduct of the EC.

10.2 Data and Safety Monitoring Board

A Data and Safety Monitoring Board (DSMB) will be appointed to monitor the key safety and efficacy outcomes at regular intervals, to safeguard the safety and interests of the study participants, and maintain/uphold the scientific merit of the study. Members of the DSMB will not be investigators of the study. The DSMB Charter document will guide the conduct of the DSMB, and will include the procedures and stopping rules for the study.

10.3 Stakeholder Committee

A Stakeholder Advisory Committee will be formed with investigators, patient partners, patient advocacy groups (i.e. Ketamine Advocacy group, NAMI), third-party payer representatives (i.e. Medical Mutual, Blue Cross). The committee will meet during the study to review study conduct and provide input on the progress of the study. The Stakeholder Committee will be involved in disseminating the final study results, information and other materials in lay language to patients/non-scientists.

10.4 Reporting Plan

Study progress reports will be presented at regular intervals to the Executive Committee, the Stakeholders Committee, the Data and Safety Monitoring Board (DSMB) and to the Cleveland Clinic and site Institutional Review Boards (IRBs). Since this is an un-blinded study, the total number of subjects enrolled in each treatment arm will be reported. The reports may include information on demographics, AEs/SAEs, significant protocol deviations, retention/withdrawals.

Table 5: Reporting Timeline		
Committee Participants Suggested Frequence		
Executive Committee	Lead PI, site-PIs	Quarterly
Data Safety Monitoring Board	DSMB Members, Lead P.I.	Twice/year
Stakeholders Committee	All Investigators, Consultants, patient advocates	Twice/year
Investigational Review Board	Cleveland Clinic and individual site IRBs	Annually or more as needed.

11. Data Handling and Record Keeping

11.1 Data Collection

Data will be collected by the study personnel at the site. Data sources include patient reports, questionnaires and available medical records. An eCRF must be completed for each randomized patient. It is the responsibility of the Investigator to ensure that the

Confidential Page **31** of **40** Protocol V7.0 16Feb2022

eCRF is completed accurately and in a timely manner. Screen failures should be recorded on the eCRF with the reason for ineligibility recorded on the screening logs.

11.2 Retention of Records

The Investigators must maintain all confidential study documentation and take measures to prevent accidental or premature destruction of these documents. Documents should be retained for a minimum of six years after the completion or discontinuation of the clinical trial. However, applicable regulatory and institutional requirements will be taken into account in the event that a longer period is required.

12. Study Monitoring

Study Monitoring Plan

C5Research is responsible for monitoring the conduct of this study. The study will be monitored according to the Monitoring Plan, and per the applicable C5Research Standard Operation Procedures for clinical monitoring. It is the responsibility of the Investigator to allocate adequate time for monitoring, to allow the monitor to access the medical records of the patients and to provide for adequate space to conduct the monitoring visit.

13. Ethical Considerations

The study protocol, consent forms, data collection forms, and recruitment materials, if applicable, will be submitted to each site's IRB. All study personnel will have completed training in the Protection of Human Subjects according to Institutional guidelines.

Institutional Review Board (IRB)

It is the investigator's responsibility to ensure that the study protocol and informed consent documents are reviewed and approved by the appropriate IRB. Each clinical site will obtain a letter of approval from the IRB before approaching participants. Sites will provide C5Research with copies of the initial IRB approval notice prior to enrolling the first patient, and subsequent renewals, as well as copies of the IRB approved consent and other IRB approved forms.

If, during the study, it is necessary to amend either the protocol or informed consent document, the investigator will be responsible for ensuring that the IRB reviews and approves the amended documents. IRB approval of any procedures must be obtained before implementing new processes or procedures.

Informed Consent Document and Process

All subjects for this study will be provided a consent form describing this study and providing sufficient information for subjects to make an informed decision. The

Confidential Page **32** of **40** Protocol V7.0 16Feb2022

informed consent document will inform patients of their right to refuse any release of their protected health information. Each clinical site, according to local IRB requirements, is allowed to modify this informed consent document and make any necessary editorial changes, as long as neither the meaning nor intent of any section is changed.

The investigator or his/her designee (i.e., research coordinator or study nurse) will inform the patient of all aspects of the study pertaining to the patient's participation in it. The process for obtaining informed consent will be in accordance with all applicable regulatory requirements. The informed consent form (ICF) must be signed and dated by the patient and the investigator or his/her designee BEFORE the patient can participate in the study. The participant will receive a copy of all signed and dated documents, and the originals will be retained in the patient's study file or medical record.

Subject Information and Consent

Each clinical site is responsible for the confidentiality of the data associated with participants enrolled in this study, in the same manner that it is responsible for the confidentiality of any patient information within its sphere of responsibility. All forms used for the study data will be identified by coded identification number, which will be generated at the clinical center, to maintain subject confidentiality. All records will be kept in locked file cabinets at the clinical centers with access limited to study staff, and all study staff will identify participants via their unique identifier. Clinical information will not be released without written permission of the participant, except as necessary for monitoring by the IRB or DSMB. The participant grants permission to share research data with these entities in the consent document. Federal regulations govern the protection of patient's rights relative to data confidentiality and use of research data.

Consent procedures and forms, and the communication, transmission and stoppage of patient data will comply with individual-site IRB requirements for compliance with The Health Insurance Portability and Accountability Act (HIPAA). The Privacy Rule of HIPAA governs the protection of an individual's identifiable health information. C5Research will ensure that clinical centers associated with the project comply with HIPAA regulations by requiring documentation from the IRBs with the appropriate authorization or consent form. C5Research will maintain copies of all relevant documents from each clinical center. If IRB approvals are not current, data will not be accepted by C5Research. A secure, electronic data management system will be used to ensure the confidentiality of electronic protected health information. All questionnaires and study related materials will be labeled with each participant's coded identification number; there will be no protected health information indicated on the forms.

14. Publication and Disclosure

The study findings will be disseminated to the public through manuscripts, scientific and patient organization led conferences, press releases and through a dedicated website. The PIs may also publicize the study findings through talks and public symposia with their local mental health advocacy organizations (NAMI, DBSA, etc.).

This study will be registered on ClinicalTrials.gov.

Confidential Page **33** of **40** Protocol V7.0 16Feb2022

15. References

- 1. Global Burden of Disease; 2004. Geneva, Switzerland: World Health Organization, 2008.

SMCQ	Squire Memory Complaint Questionnaire	Self-report of memory issues before and after ECT (5 mins)	
PGI-Sand PGI-I	Patient Global Impression Scale for Severity and Improvement for Depression	7 point scales assessing improvement and severity of depression (2 mins)	
QOLS	Quality of Life Scale	Self-reported questionnaire that measures quality of life in 8 domains (5 mins)	
PRISE	Patient Rated Inventory of Side Effects	Self-report of adverse events specific to nine organ or function systems (<5 mins)	
Treatment Preference	Treatment Preference	7 point scale assessing preference for either study treatments	
	CLINICIAN RA	TED SCALES	
MADRS	Montgomery Asberg Depression Rating Scale	Measures severity of depression symptoms including sadness, concentration, sleep, and disruptive thoughts (10-20 mins)	
CSSRS	Columbia Suicide Severity Rating Scale	Assessment of suicidal ideation (10 mins)	
CADSS*	Clinician Administered Dissociative Symptoms Scale	Dissociative symptom scale to be administered post- treatment (10 mins)	
YMRS	Young Mania Rating Scale	Measures symptoms of mania (10 mins)	
BPRS*	Brief Psychiatric Rating Scale	Measures positive symptoms of psychosis (5 mins)	
CGI-S and CGI-I	Clinical Global Impression Scale for Severity and Improvement	Scales to record global clinical impression by a clinician regarding improvement and severity of patients mental condition (5 mins)	
	COGNITIVE	TESTING	
MoCA	Montreal Cognitive Assessment	Tests cognitive function covering 8 cognitive domains including visuospatial assessment, short-term memory and working memory (10 mins)	
COWAT	Controlled Oral Word Association Test	Verbal fluency test that measures spontaneous production of words belonging to the same category or beginning with the same letter (5- 10 mins)	
HVLT-R	Hopkins verbal Learning Test - Revised	Verbal learning and memory test with six alternate forms (10 mins)	
Stroop	Stroop Color Word Test	Measures processing speed and selective inhibition (5 mins)	
NAART	North American Adult Reading Test	Estimate of premorbid intellectual ability (3 mins)	
CPFQ	Cognitive and Physical Functioning	Assessment of motivation, energy level, & mental acuity (5 mins)	

Schedule of Events (ECT Arm)

Visit	Screening (Maximum of 28 days)	Randomization (within 1 week after eligibility is confirmed)	Treatment Phase (Up to 9 treatments over 3- 5 weeks)									EOT (within 3 days after last treatment)
			Baseline / V1	V2	V3	V4	V ₅	V6	V7	V8	V9	
Informed consent	X		,									
Eligibility Criteria	X											
Demographics	X											
Medical history	X		X	X	X	X	X	X	X	X	X	X
Urine pregnancy test	X											
Vitals (BP, heart rate, weight)			X	X	X	X	X	X	X	X	X	BP, HR
Randomization		X										
Psychiatric Evaluation	X		X	X	X	X	X	X	X	X	X	X
ECT			X	X	X	X	X	X	X	X	X	
Psychiatric Medication Log	X		X	X	X	X	X	X	X	X	X	X
Somatic Therapies Log	X		X	X	X	X	X	X	X	X	X	X
Evaluate for AEs/SAEs			X	X	X	X	X	X	X	X	X	X
Diagnostic Interview												
MINI 7.0.2	X											
Patient Rated Scales												
QIDS-SR-16			X	X		X		X	X		X	X

Schedule of Events (ECT Arm)

Visit	Screening (Maximum of 28 days)	Randomization (within 1 week after eligibility is confirmed)	(Up to 9 treatments over 3- 5 weeks)									EOT (within 3 days after last treatment)
			Baseline/ V1	V2	V3	V4	V ₅	V6	V7	V8	V9	
GSE-MY				X		X		X	X		X	X
SMCQ			X	X		X		X	X		X	X
PGI-S			X	X		X		X	X		X	X
PGI-I				X		X		X	X		X	X
QOLS			X	X		X		X	X		X	X
PRISE			X	X		X		X	X		X	X
CPFQ			X	X		X		X	X		X	X
Treatment Preference												X
Clinician Rated Scales												
MADRS	X		X	X		X		X	X		X	X
CSSRS			X	X		X		X	X		X	X
YMRS	X		X	X		X		X	X		X	X
BPRS*			X	X		X		X	X		X	X
CGI-S**			X	X		X		X	X		X	X
CGI-I**				X		X		X	X		X	X
CADSS*			X	X		X		X	X		X	X
Cognitive Assessments												
MoCA	X											X
COWAT			X			1						X
HVLT-R			X									X
Stroop			X									X
NAART			X									

^{*}CADSS and BPRS to be administered post treatment.
**CGI-S and CGI-I to be performed by psychiatrist.

Schedule of Events (Ketamine Arm)

Visit	Screening (Maximum of 28 days)	Randomization (within 1 week of confirmed eligibility)	Treatment Phase (Up to 6 treatments over 3-5 weeks)						EOT (within 3 days after last treatment)
			Baseline/V1	V2	V3	V4	V5	V6	
Informed consent	X								
Eligibility Criteria	X								
Demographics	X								
Medical history	X		X	X	X	X	X	X	X
Urine pregnancy test	X								
Vitals (BP, heart rate, , weight)			X	X	X	X	X	X	BP, HR
Randomization		X							
Psychiatric Evaluation	X		X	X	X	X	X	X	X
Ketamine Infusion			X	X	X	X	X	X	
Psychiatric Medication Log	X		X	X	X	X	X	X	X
Somatic Therapies Log	X		X	X	X	X	X	X	X
Evaluate for AEs /SAEs			X	X	X	X	X	X	X
Diagnostic Interview									
MINI 7.0.2	X								
Patient Rated Scales									
QIDS-SR-16			X	X	X	X	X	X	X

Schedule of Events (Ketamine Arm)

Visit	Screening (Maximum of 28 days)	Randomization (within 1 week of confirmed eligibility)		EOT (within 3 days after last treatment)					
			Baseline/V1	V2	V3	V4	V5	V6	
GSE-MY				X	X	X	X	X	X
SMCQ			X	X	X	X	X	X	X
PGI-S			X	X	X	X	X	X	X
PGI-I				X	X	X	X	X	X
QOLS			X	X	X	X	X	X	X
PRISE			X	X	X	X	X	X	X
CPFQ			X	X	X	X	X	X	X
Treatment Preference									X
Clinician Rated Scales									
MADRS	X		X	X	X	X	X	X	X
CSSRS			X	X	X	X	X	X	X
YMRS	X		X	X	X	X	X	X	X
BPRS*			X	X	X	X	X	X	X
CGI-S**			X	X	X	X	X	X	X
CGI-I**				X	X	X	X	X	X
CADSS*			X	X	X	X	X	X	X
Cognitive Assessments									
MoCA	X								X
COWAT			X						X
HVLT-R			X						X
Stroop			X						X
NAART			X						

^{*}CADSS and BPRS to be administered post treatment.
**CGI-S and CGI-I to be performed by psychiatrist.

Schedule of Events (Follow-Up Phone Call – Non-Responders)

Visit	Month 1 (+/- 2 weeks)
Evaluate for AEs/SAEs	X
Evaluate for additional ECT, ketamine, psychotropic treatment(s)	X
Patient Rated Scales: PGI-S & PGI-I	X
Complete QIDS Form	X
Complete MADRS Form	X

Schedule of Events (Follow-Up Visits – Responders will occur through Month 1 Follow-Up at a minimum)

•	Month 1	Month 3	Month 6
Visit	(+/- 2 weeks)	(+/- 2 weeks)	(+/- 2 weeks)
Update Medical History	X	X	X
Vitals (BP, heart rate, weight)	X	X	X
Psychiatric Evaluation	X	X	X
Psychiatric Medication Log	X	X	X
Somatic Therapies Log	X	X	X
Evaluate for AEs/SAEs	X	X	X
Patient Rated Scales			
QIDS-SR-16	X	X	X
GSE-MY	X	X	X
SMCQ	X	X	X
PGI-S & PGI-I	X	X	X
QOLS	X	X	X
PRISE	X	X	X
CPFQ	X	X	X
Clinician Rated Scales			
MADRS	X	X	X
CSSRS	X	X	X
YMRS	X	X	X
BPRS	X	X	X
CGI-S & CGI-I*	X	X	X
CADSS	X	X	X
Cognitive Assessments			
MoCA	X	X	X
COWAT	X	X	X
HVLT-R	X	X	X
Stroop	X	X	X

^{*}To be performed by psychiatrist.

ELEKT–D: Electroconvulsive therapy (ECT) vs. ketamine in patients with treatment resistant depression (TRD)

Statistical Analysis Plan

Version 2.0 07/01/2022

ELEKT-D is an open label, multi-center clinical trial to compare electroconvulsive therapy (ECT) with ketamine (KET) in patients with treatment resistant depression (TRD). The specific study aims include:

- Aim 1: to investigate the comparative effectiveness of ECT and ketamine on measures of depression.
- Aim 2: To investigate the relative impact of ECT and ketamine on measures of memory and cognitive function.
- Aim 3: To investigate the relative impact of ECT and ketamine on patient reported QoL measures after acute treatment and at follow-up over six months.

Table 1 below lists the primary, secondary and safety endpoints measured from the study participants. More details and the measurement schedules of these endpoints are described in the study protocol.

Analysis of baseline characteristics. The analysis will be based on the randomized population (i.e., all participants randomized). Participant characteristics at baseline will be summarized as descriptive statistics (mean, standard deviation [SD], median, inter-quartile range, or range for continuous data, and count and percentage for categorical data). The baseline characteristics will be compared between the two study groups using the t-test, the Wilcoxon rank sum test, or the chi-squared test as appropriate.

Analysis of primary endpoint. The primary endpoint of the trial is treatment response, which is defined as $a \ge 50\%$ decrease in QIDS-SR-16 scores from the baseline visit/visit 1 to the end of treatment visit in the acute phase. The study hypothesis is that the response rate of ketamine is non-inferior to ECT with a margin of -10%, that is,

$$H_0: P_k - P_e \le -10\%$$
 vs. $H_1: P_k - P_e \ge -10\%$

where P_k represents the response rates in the ketamine group, and P_e represents the response rate in the ECT grou; H_0 and H_1 denote the null and alternative hypotheses, respectively. The primary endpoint of treatment response will be summarized as proportions, along with 95% confidence intervals, for each treatment group. The Farrington-Manning score test will be then used to compare the response rates between ECT and KET at an inferiority margin of -10% (ketamine minus ECT) and a one-sided type I error of 0.025. The difference of the two response rates will be also reported with the 95% confidence interval.

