5.4 Randomization of Patients

All patients who are eligible for the trial will be randomized in a 1:1 fashion to either ECT or ketamine treatment. Given the nature of these treatments, treatment arms cannot be blinded at the patient or clinician level. Randomization will be conducted centrally through a secure electronic data management system. Detailed instructions can be found in the Manual of Operations (MOP). Collect patient status as inpatient or outpatient at randomization.

6. Study Treatments

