Sample size justification. For the outcome measure of QIDS-SR16 in TRD patients in standard anti-depressant analyses, an overall response rate of 47% was reported in the STAR*D study [1]. Zarate et al. showed that a 71% response rate of ketamine on HAMD-21 was associated with patients with major depression [2]. Murrough et al. reported a 64% response rate of ketamine on MADRS in patients with TRD [3]. Other studies revealed response rates of ketamine ranging from 50% to 90% in patients with TRD [4-14]. Janicak et al. reported a 56% response rate of ECT on HAMD-24 in patients of major depression [15]. Our preliminary internal data showed 45.8% patients as responders in the ketamine group, and 45.1% patients as responders in the ECT group, using clinician rated MADRS scales. The patients in the ketamine group were resistant to ECT treatment and still had a comparable response rate as ECT. For the ELEKT-D study, patients do not have to be ECT resistant, and hence the ketamine response rate is expected to be even higher. Based on the above data from the previous studies and our pilot study, we assume a 50% response rate for ECT patients. At a non-inferiority margin of 10% (i.e. response rate of ketamine is at most 10% lower than ECT) and a one-sided alpha value of 0.025, a total sample of 346 is needed to provide 80% power using the Farrington-Manning score test of risk difference if the actual difference is +5% (i.e. response rate of ketamine is 5% higher than ECT). If the actual difference is +10%, the statistical power would increase to 96.4% with the same sample size; if the non-inferiority margin is reduced to 5%, then the power will be 80.3%. Assuming an attrition rate of 15%, a total number of 400 subjects (200 per treatment group) are then required.

References

[2] Zarate CA Jr., Singh JB, Carlson PJ, et al. A randomized trial of an N-methyl-D-aspartate antagonist in treatment-resistant major depression. Arch Gen Psychiatry. 2006; 63(8):856–864.

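### The primary non-inferiority test uses no baseline variable and the protocol's supplementary logistic model is absent for that endpoint; the test is valid, but a modest gain in precision may be lost

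*SAP*

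**What the plan says.** **Primary test.** The SAP, under Analysis of primary endpoint, says "The Farrington-Manning score test will be then used to compare the response rates between ECT and KET". The margin is −10 points for ketamine relative to ECT, tested one-sided at 0.025. The SAP also reports each arm's response rate and the difference, with 95% confidence intervals. No covariate or stratification factor is named. The sensitivity analyses change only how missing outcomes are filled in. Baseline variables enter the multiple-imputation model, but the same unadjusted test is then applied to each imputed dataset.

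**Adjustment elsewhere in the SAP.** Site is a fixed effect in the linear mixed models under Analysis of secondary endpoints. Those models may also take in baseline characteristics that turn out to differ significantly between arms, if this is thought necessary. Logistic regression is mentioned only under secondary endpoints. Heterogeneity is examined by one-factor subgroups with Breslow-Day tests. Inpatient status appears in no SAP analysis and is not in the subgroup list.

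**Protocol.** Section 9 compares response rates with a chi-square test, which is also unadjusted. It then adds: "A multivariable logistic regression model will be constructed, to account for potential heterogeneity of treatment effect caused by confounding variables". No covariates are listed. The SAP's summary of changes does not mention this model.

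**Variables available.** Protocol section 5.4 instructs: "Collect patient status as inpatient or outpatient at randomization". MADRS is scored at screening (sections 5.2 and 7.1), where demographics are also taken. Section 7.1 places randomisation after screening and schedules Baseline/Visit 1 according to the allocated arm, so the Visit 1 QIDS-SR-16 is completed after open-label allocation.

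**Sizing.** The SAP says "we assume a 50% response rate for ECT patients" and "a total sample of 346 is needed to provide 80% power using the Farrington-Manning score test of risk difference", for a true difference of +5 points. It allows 15% attrition and enrols 400.

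**The concern.** When baseline variables predict response, an analysis that uses them gives a narrower interval for the risk difference. In a non-inferiority trial the interval's lower limit decides the result, so its width matters directly. The SAP leaves such variables out of the one comparison that decides the trial, yet adjusts the same scale for site in a secondary model.

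The second issue is prespecification. The protocol promised a regression for the primary outcome and the SAP contains none. The SAP's only rule for adding patient characteristics to a model depends on observed imbalance. Any adjusted primary result presented later would therefore look data-driven. This holds whatever the covariates' prognostic strength.

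At stake is a modest amount of power in a scenario planned at about 80%, together with a gap between protocol and SAP that readers will notice.

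**Working it through.** **Inputs from the SAP.** ECT response 50%; ketamine 55% (difference +5 points); margin 10 points; one-sided alpha 0.025; 346 evaluable (173 per arm); 400 enrolled; 15% attrition.

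**Input that is an assumption.** R², the share of outcome variance explained by the covariates. The documents give no value. The range used is 0 to about 0.14.

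**Step 1: reproduce the plan's figures.** The Farrington-Manning restricted proportions under the null are 0.4743 (ketamine) and 0.5743 (ECT).

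- s0 = √(0.4743×0.5257 + 0.5743×0.4257) = 0.7027
- s1 = √(0.55×0.45 + 0.50×0.50) = 0.7053
- n per arm = (1.960×0.7027 + 0.8416×0.7053)² / 0.15² = 172.6, rounded up to 173, total **346**, as stated.

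Power = Φ[(0.15√n − 1.960×s0)/s1]:

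- n = 173: Φ(0.844) = **80.1%** (SAP: 80%).
- n = 170, since 400 × 0.85 = 340: Φ(0.820) = **79.4%**.
- n = 200 (all 400 evaluable): **85.4%**.

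The same method at a true difference of +10 points gives 96.4%, matching the SAP: "If the actual difference is +10%, the statistical power would increase to 96.4% with the same sample size".

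**Step 2: ideal gain from adjustment.** If the variance of the risk difference falls by the factor (1 − R²), n is replaced by n/(1 − R²).

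| Assumed R² | Power at 346 | Power at 340 | 340/(1 − R²) |
|---|---|---|---|
| 0 | 80.1% | 79.4% | 340 |
| 0.03 | 81.3% | 80.6% | 351 |
| 0.05 | 82.0% | 81.4% | 358 |
| 0.10 | 84.0% | 83.4% | 378 |

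This is an upper view, because it ignores the cost of estimating the coefficients.

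**Step 3: simulation that includes that cost.** Logistic standardisation to a marginal risk difference was compared with the unadjusted test: 346 patients, a severity score, inpatient status and five sites as covariates, 20,000 replicates per row.

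| R² | Adjusted | Unadjusted | Difference (points) |
|---|---|---|---|
| 0 | 79.5% | 80.9% | −1.5 |
| 0.033 | 80.6% | 80.9% | −0.3 |
| 0.058 | 82.0% | 81.3% | +0.7 |
| 0.095 | 83.1% | 80.9% | +2.1 |
| 0.139 | 84.9% | 80.6% | +4.3 |

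Differences were taken before rounding. The one-sided type I error of the adjusted analysis was 2.4% to 2.6%.

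A second simulation added age and used 340 patients and 8,000 replicates. Each adjusted range is with and without a degrees-of-freedom correction to the variance.

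| R² | Adjusted | Unadjusted |
|---|---|---|
| 0 | 78.6–79.5% | 80.2% |
| 0.028 | 80.1–80.7% | 80.2% |
| 0.054 | 80.6–81.3% | 80.4% |
| 0.086 | 82.4–83.1% | 80.4% |

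**Step 4: read the results together.** At R² near 0.03 the formula suggests 351 − 340 = 11 patients' worth of information, but the simulations show no dependable gain there. At R² of 0.05 to 0.10 the formula gives +2 to +4 points and the simulations mostly less. A fair summary is about 1 to 4 points. With covariates that predict nothing, about 1 point is lost.

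**The case against.** The strongest reply is that nothing is wrong with the planned test. It is a valid comparison of randomised arms on the scale of the margin, the sample was sized for that same test, and the sizing reproduces. Chance imbalance is not bias, because the interval already allows for it. All of this stands.

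A reader might infer that the protocol's primary test was adjusted and that the SAP weakened it. The documents do not support that. The protocol's test was an unadjusted chi-square, and its regression was aimed at heterogeneity and confounding, not precision. As written, the regression would usually yield a conditional odds ratio, which cannot be judged against a −10-point margin. Leaving it out therefore cost the primary test no precision. What remains is an unexplained difference between the documents.

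A reader might also infer that adjustment costs nothing, or that the trial is underpowered without it. Neither follows. No prognostic strength is documented, response is already a change from each patient's own baseline, and the simulations show a small loss at R² of zero. The figure near 80% belongs to one scenario: power is 96.4% at +10 points, and 85.4% at +5 if all 400 are evaluable.

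Finally, SAP version 2.0 was drafted at the end of an open-label study, so choosing covariates at that stage adds discretion. This is a fair caution. It is met by fixing a short list before the analysis, drawn from variables recorded before treatment, rather than by leaving adjustment to observed imbalance.

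**Conclusion.** The point holds as a missed efficiency and a gap in prespecification, not as an error in the test or the sample size. The primary analysis uses no baseline variable although suitable ones are collected before treatment. The protocol's supplementary logistic model is not carried into the SAP for this endpoint, and no reason is given.

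In the SAP's main scenario (ECT 50%, true difference +5, margin 10 points), adjustment would change power by about +1 to +4 points if R² is 0.05 to 0.10, by about zero at 0.03, and by about −1 point if the covariates are not prognostic. Every one of these figures rests on an assumed R². The case for prespecifying one adjusted analysis, and for explaining the change from the protocol, does not.

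**What to change.** Before the analysis, add to the SAP:

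1. A logistic model of response on arm, site, inpatient/outpatient status, screening MADRS and age, in the same population as the planned primary analysis. Standardise it to a marginal risk difference (ketamine minus ECT) with a 95% confidence interval, judged against −10%.
2. The Farrington-Manning test, reported alongside. Say in advance that the adjusted interval decides the claim, so that two results cannot compete.
3. Screening MADRS as the severity covariate, because the Visit 1 QIDS-SR-16 follows open-label allocation.
4. The variance method for the standardised difference, and a rule for pooling very small sites.
5. One line saying why the protocol's logistic model is replaced: its covariates were not named, and an odds ratio does not address the margin.

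The cost is SAP text and one more model on data already collected. The downside is a possible loss of about 1 point of power if the covariates are weak. The analysis that decides the claim would also no longer be the exact test used for sizing, which the SAP should acknowledge.
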